#### 2. Purpose

#### 2.1. Purpose of this project including research questions and/or aims

The primary objective of this pilot study is to assess the efficacy of a MD intervention (education + EVOO and mixed nut supplementation) versus that of an AHA nutrition intervention (education) on serum blood lipid levels as markers for cardiovascular disease risk. As secondary outcomes we will assess insulin resistance, serum metabolic factors, blood pressure, body mass index, and waist circumference.

Research Question: In the Southeastern United States, is the dietary pattern of the American Heart Association or a Mediterranean style diet more effective in the reduction of CVD risk factors.

Aim 1: To assess whether or not patients have improvements in their CVD risk factors by the end of the 12-week program.

Aim 2: To assess which dietary intervention is most effective in the reduction of CVD risk factors at the end of the 12-week program.

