  - 5. Individuals who anticipate absence or travel throughout the study that would interfere with their ability to complete the analysis at the mid-point and end of challenge.
  - 6. Patients with a peanut, tree nut, or olive oil food allergy or intolerance.
  - 7. Patients who are unable or unwilling to travel to Auburn University main campus for live health and wellness challenge events, individual assessments, personal appointments, and pre- and post- data collection
  - 8. Individuals who have NOT been stabilized on medication to treat or manage high blood pressure, high cholesterol, dyslpidiemia, or pre-diabetes for at least 12 weeks prior to the study.
  - 9. Patients who do not have access to the internet and therefore unable to complete the education portion of the study
  - 10. Individuals who have a pacemaker
  - 11. Patients who decline participation during informed consent

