# **Total Participant Involvement Time**

#### 340 minutes

- 5) STUDY REQUIREMENTS
  - a) The participants will be asked to follow a dietary pattern that is associated with their assigned intervention group. The Mediterranean Diet (MD) group will be given supplements of extra virgin olive oil (EVOO) and mixed nuts. Participants in this group will be asked use these supplements as a part of their daily intake. A total of 6 L of EVOO and 6 pounds of mixed nuts (3 pounds raw walnuts and 3 pounds raw almonds) will be administered throughout the study. Participants in the MD group will be given 3 L of EVOO and 3 pounds of mixed nuts at the baseline appointment asked to return unused portions of at their 6-week appointment. At that time they will be given a new supplementation of 3 L or EVOO and 3 pounds of mixed nuts. Participants will be given the same instructions for use and asked to return unused portions at the end of the study (week 12).
  - b) The participants might have follow-up appointments scheduled with the pharmacist within the AUPCC depending on the patient's personal care plan that is developed at baseline. For instance, if a patient has potential or actual drug-related problems that are identified on their baseline MTM appointment, then the pharmacist will schedule follow-up appointments that are appropriate for the problem and the plan of care that is developed to address these problems. This will be done consistently between all patients in the study, regardless of the randomization (the pharmacist and the will be blinded concerning which group the patient is randomized to concerning dietary intervention).
  - c) Narrated nutrition education presentations will be developed by a registered dietitians, dietetic interns, graduate students, and faculty. These presentations will be loaded on the "Healthy Hearts Program" website. The participants will be asked one presentation weekly for the first 6 weeks of the study and then one additional education module at week 9. A post-presentation assessments will load after the presentation is completed, and completion of the assessment will be used as verification that the participant watched the presentation.
  - d) The participant will complete the following at baseline, week-6 and week 12 of the study: Diet History Questionnaire II, International Physical Activity Questionnaire, and a Mediterranean diet knowledge and adherence questionnaire.

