# **Venipuncture blood draw-** *Phlebotomy procedures will follow the World Health Organization's Guidelines on drawing blood: Best practices (6)*

- 1) **Overview**: Participant will be instructed not to eat or drink anything, other than water, after midnight the day of their baseline, 6-week, and 12-week visits. Phlebotomy of a peripheral arm vein will be performed by AUPCC clinicians (pharmacists and pharmacy residents) who have been phlebotomy trained, using sterile procedures and seated position. A sterile bandage will cover the phlebotomy site after the procedure and arm will be elevated to ensure that bleeding has stopped. The participant will be observed for any lightheadedness, bruising or bleeding during and after the procedure.
  - a) If the participant is lightheaded, he/she will be reclined until symptoms resolve

- b) If the participant is asymptomatic after the phlebotomy procedure, he/she will be released
- c) A maximum of 3 attempts to access a vein will be allowed at each visit, for each participant. If 3 unsuccessful attempts to access a vein are made, the participant will be excused from this portion of the study.

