#### 4.4. Data collection instruments

 Clinical Data Recording Form (height measurement (inches), change in baseline body weight (%), change in total body weight (kg), Calculated BMI (kg/m2) measurement of body composition (using bioelectrical impedance analysis) (% body fat, pounds of fat, pounds of lean mass, pounds of total body water), waist measurement (inches), hip measurement (inches), Waist to Hip Ratio, Systolic blood pressure (mmHg), Diastolic blood pressure (mmHg), resting pulse (bpm), fasting blood glucose (mg/dL), fasting total cholesterol (mg/dL), fasting LDL-cholesterol (mg/dL), fasting HDL-cholesterol (mg/dL), fasting Triglycerides (mg/dL), total Cholesterol to HDL ratio, and ASCVD Score (%)), fasting insulin mI/L, fasting leptin ng/mL, IL-6 (pg/mL), tumor necrosis factor-α (pg/mL), urinary tyrosol and hydroxytyrosol.

- 2) International Physical Activity Questionnaire
- 3) Mediterranean Diet Nutrition Adherence and Knowledge Questionnaire
- 4) Diet History Questionnaire II (DHQ II)

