The Diet History Questionnaire II, International Physical Activity Questionnaire, and the Mediterranean Knowledge/Adherence questionnaire will be collected at the beginning, mid-point and the end of the study. The number of drug-related problems identified through Medication therapy management will be collected at the beginning and end of the study

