### 5. Risks and Discomforts

5.1. Description of potential risks that participants may encounter

Physical Risk: Blood draw (venipuncture phlebotomy)- Patients will have approximately 10 mL of blood taken a total of three times (total 30 mL or 2 tablespoons over 12 weeks) throughout this study (baseline, week 6, and week 12). The blood will be taken via venipuncture phlebotomy of the arm. Risks include: pain or discomfort at the site of puncture; bruising at point of blood draw; redness and swelling for the vein; rarely an infection; and, uncommonly, faintness from the procedure. See Appendix G "Measurement Procedures."

Breach of confidentiality: Investigators will be accessing confidential or identifiable data of participants. Precautions described below.

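### The visible protocol lists no symptom or tolerability item for either arm, and states none before oil and nuts are issued again at week 6

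*Combined protocol and SAP*

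**What the plan says.** **Supply.** Section 4.2, item 5(a) sets the amounts for the MD arm: "A total of 6 L of EVOO and 6 pounds of mixed nuts (3 pounds raw walnuts and 3 pounds raw almonds". Half is issued at baseline. Of the week 6 appointment the protocol says: "At that time they will be given a new supplementation of 3 L or EVOO and 3 pounds of mixed nuts". The only other product step stated for that visit is the return of what was not used.

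**Outcomes.** Section 2.1 makes serum lipids primary and adds: "As secondary outcomes we will assess insulin resistance, serum metabolic factors, blood pressure, body mass index, and waist circumference".

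**Instruments.** Section 4.4 lists four. The first begins "Clinical Data Recording Form (height measurement (inches), change in baseline body weight (%), change in total body weight (kg" and continues with body composition, blood pressure, pulse, laboratory values and the ASCVD score. The other three cover physical activity, Mediterranean diet adherence and knowledge, and diet history.

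**Analysis.** Section 4.5 analyses these measurements and closes with: "The number of drug-related problems identified through Medication therapy management will be collected at the beginning and end of the study".

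**Harm.** Section 5.1 names one physical risk: "Physical Risk: Blood draw (venipuncture phlebotomy)- Patients will have approximately 10 mL of blood taken a total of three times". For that procedure, section 4.3 states: "The participant will be observed for any lightheadedness, bruising or bleeding during and after the procedure". For the supplied foods, the protection in the visible text is exclusion 6 in section 3.1: "Patients with a peanut, tree nut, or olive oil food allergy or intolerance".

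**The concern.** Exclusion 6 shows that the protocol regards the supplied foods as a possible hazard. An entry exclusion removes only people who already know of an allergy or intolerance. It cannot detect a reaction that first appears on study.

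A symptom that nobody asks about at weeks 6 and 12 cannot be reliably reconstructed by the analysts afterwards. Aim 2 asks which diet works better, and only one arm is given food. The trial could therefore report a benefit of the MD package with no matching account of how well each programme was tolerated.

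Week 6 matters most. It is the one scheduled visit at which a participant has experience of the foods and is about to receive more of them.

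**Working it through.** The protocol gives no figure to reproduce on this point: there is no sample size, power statement or expected reaction rate. The check is a reading of each place where a tolerability item could stand, plus simple counts.

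**1. Form items (section 4.4), each named quantity counted once.**
- Height, weight change in %, weight change in kg, BMI: 4
- Body composition values: 4 (running total 8)
- Waist, hip, waist-to-hip ratio: 3 (11)
- Systolic pressure, diastolic pressure, pulse: 3 (14)
- Fasting glucose: 1 (15)
- Total, LDL and HDL cholesterol, triglycerides: 4 (19)
- Cholesterol-to-HDL ratio, ASCVD score: 2 (21)
- Insulin, leptin, IL-6, TNF-α: 4 (25)
- Urinary tyrosol, hydroxytyrosol: 2 (27)

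Symptom or reaction items: 0 of 27.

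**2. Each place side by side.**

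| Place | Symptom or tolerability item stated? |
|---|---|
| Four instruments (4.4) | None described, 0 of 4 |
| Primary and secondary outcomes (2.1) | No |
| Analysis variables (4.5) | No. The nearest is the drug-related problem count, at beginning and end only |
| Physical risks (5.1) and precautions (5.2) | Blood draw only |
| Observation for harm (4.3) | Blood draw only |
| Week 6 product steps (4.2, items 3(d) and 5(a)) | Return of unused product and re-issue only |
| Visits after product is issued (weeks 6 and 12) | No stated question, 0 of 2 |

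**3. Exposure.**
- Share issued at week 6: 3/6 L = 50% of the oil and 3/6 lb = 50% of the nuts.
- Time from first issue to the next visit scheduled for everyone: 6 × 7 = 42 days.
- If a six-week supply were used in full: 3000 mL / 42 = about 71 mL of oil a day. With 3 lb = 1361 g, 1361 / 42 = about 32 g of nuts a day. Full use is an assumption. Unused product is returned, and the written consumption goals are not visible.

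**4. Routes by which a complaint could still be captured.**
- Medication therapy management (MTM) takes place at baseline and again for all participants at weeks 6 and 12 (section 4.2, item 5(g)). Its baseline scope includes advice on supplements.
- Section 4.2, item 3(c) sends subjective as well as objective appointment information to the medical record. A code list links that record to the study code.
- Section 6.1 promises access to a dietitian throughout.

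These routes can receive a complaint. None of them defines a variable that would bring it into a comparison of the arms.

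**5. Added time.** Assuming 1 to 2 minutes at each of 2 visits, the total is 2 to 4 minutes. Section 4.2, item 4 gives 180 in-person minutes: 2/180 = 1.1% and 4/180 = 2.2%.

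**The case against.** The strongest reply is that capture already exists. Every participant has an MTM consultation at weeks 6 and 12, what patients report goes into a permanent record, and that record can be linked to the study code. The protocol's silence on what is asked at week 6 does not show that nothing is asked. This stands, and it rules out the tempting reading that the trial has no safety monitoring or could not learn of a reaction. Medication safety and blood-draw harms are both covered, and a volunteered complaint could be retrieved. What is missing is a planned question and a variable to hold the answer.

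A reader might also infer that blinding stops the pharmacist from asking. The documents do not support that, because a neutral question needs no knowledge of the arm. Nor does the supply schedule oblige staff to re-issue a food that someone has not tolerated. It simply states no check.

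Consent pages, appendices, written consumption instructions, the health interview and the questionnaires are not visible. A stop-and-report instruction could well be in one of them. The point is therefore confined to the visible text. Section 5.1 is visible, and its list of risks omits the foods.

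Finally, these are ordinary foods, people with known allergy or intolerance are excluded, and counts in a pilot would not estimate a rate precisely. All of this is correct and keeps the weight of the point low.

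**Conclusion.** The point holds as a minor safety and reporting improvement. In the visible protocol, 0 of 4 instruments is described as having a symptom or tolerability item, 0 of 27 form quantities is one, and neither visit after product is issued has a stated question. Half of all supplied food goes out at week 6 without a stated check. Followed as written, the plan yields no tolerability summary by arm.

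The omission does not touch the lipid comparison. With no reaction rate and no sample size in the documents, no expected number of reactions can be given. The gain is protection of participants at week 6 and a complete descriptive record. The conclusion assumes that no unseen document already asks the question. If one does, citing it and adding the table by arm would close most of the gap.

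**What to change.** 1. At weeks 6 and 12, the dietitian or nutrition student who already gives the in-person questionnaires (section 4.3) asks both arms one identical, neutral question on new symptoms or reactions since the last visit. At week 6 this comes before any hand-out.
2. Log the answer under the study code, on a sheet kept away from the blinded pharmacists, since pharmacists and residents also take the outcome measurements.
3. If an MD participant reports a reaction to a supplied food, do not re-issue that food. Refer through the existing clinic route, note any unblinding, and keep the participant in follow-up.
4. Give any instruction to stop and report between visits to both arms in neutral terms. Do not repeat the allergy screen in the MD arm alone. Prompting one arm would distort the comparison of reported symptoms.
5. Tabulate reported symptoms by arm, and foods withheld, descriptively and without a test.
6. Add the supplied foods as a risk in section 5.1.

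The cost is a short amendment, one log sheet and an estimated 2 to 4 minutes per participant. The downsides are slightly lower exposure in a few MD participants, which should be reported, and occasional unblinding when a reaction needs clinical attention.

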### 5. Risks and Discomforts

5.1. Description of potential risks that participants may encounter

Physical Risk: Blood draw (venipuncture phlebotomy)- Patients will have approximately 10 mL of blood taken a total of three times (total 30 mL or 2 tablespoons over 12 weeks) throughout this study (baseline, week 6, and week 12). The blood will be taken via venipuncture phlebotomy of the arm. Risks include: pain or discomfort at the site of puncture; bruising at point of blood draw; redness and swelling for the vein; rarely an infection; and, uncommonly, faintness from the procedure. See Appendix G "Measurement Procedures."

Breach of confidentiality: Investigators will be accessing confidential or identifiable data of participants. Precautions described below.

#### 5.2. Description of precautions taken to eliminate or reduce potential risks

Venipuncture phlebotomy precautions: Verbal and written consent will be received from each patient. Patient will receive verbal and written risks of procedure. All venipuncture guidelines will be followed as outlined in protocol.

Patient data is stored securely in the electronic medical record (EMR). Access to the EMR is restricted to individual account holders assigned by the clinic in a password-protected program. When recorded into the clinical data recording form, data will be recorded confidentially with a numbered linkage back to the patient. No personally identifiable information will be recorded with the associated patient data. All information linking patients and data will be stored in a locked cabinet in a controlled access medical records room.

All surveys and questionnaires will remain anonymous and have no identifiable patient information. Patients' data from survey collection will remain confidential through the use of Qualtrics for delivery of the surveys.

### 6. Benefits

# 6.1. Description of direct benefits to participants by participating in this study

This study should have benefits on participants' CVD risk. They should see decreases in their blood pressure, blood glucose, total cholesterol, and blood pressure after completion.

All participants will receive free nutrition education and access to a registered dietitian throughout the study. Both groups will receive nutrition education on dietary interventions that studies have shown decrease the risk of CVD. Therefore, benefits include, obtaining the nutritional knowledge to change dietary patterns for the reduction of CVD risk factors.

# **6.2.** Description of benefits for the general population that may be generated from this study

This study should have benefits on participants' CVD risk. They should see decreases in their blood pressure, blood glucose, total cholesterol, and blood pressure after

completion. Participants will also gain insight into proper dietary patterns for the reduction of CVD risk factors.

